11.4.1.3. Exploratory Efficacy Analyses

The exploratory efficacy analyses include subgroup analyses of the primary and secondary endpoints and analyses of exploratory efficacy endpoints. Any additional analysis plans will be specified in the SAP.

11.4.1.3.1. Subgroup Analyses

The subgroup analyses for ORR, duration of response, DCR, CBR, PFS, and OS will be performed. Subgroup analyses will include:

- ERs (positive, negative).
- Progesterone receptors (positive, negative).
- Lines of prior systemic therapy not including hormone therapy (<3 , ≥ 3).
- Prior pertuzumab (yes, no)
- Prior pertuzumab in 1st or 2nd line in advanced/metastatic breast cancer (yes, no)
- Renal impairment at baseline (within normal range, mild/moderate impairment)
- Hepatic impairment at baseline (within normal range, mild-moderate impairment)
- Best response to T-DM1 therapy (CR/PR/SD, PD).
- Brain metastases (brain metastases, no brain metastases)
- Age (<65 , ≥ 65 years).
- Race (Asian, others).
- Region (Asia, rest of world).
- Ethnicity (Hispanic/Latino, others).
- ECOG PS (0, 1).

The subgroups are based on baseline values (ie, the last non-missing values before the first drug administration). In each subgroup defined above, the analysis will be carried out using the same type of methodology as described for the overall analysis of the corresponding endpoint. These results will be considered exploratory because of smaller sample sizes that cannot be pre-specified.

11.4.1.3.2. Analyses of Exploratory Efficacy Endpoints

Duration of stable disease, time to response, exposure-response relationships for efficacy and safety endpoints, and potential biomarkers of response, such as serum HER2ECD concentrations, will be evaluated and considered as exploratory efficacy endpoints.

Duration of stable disease and time to response will be summarized with median event times and their 2-sided 95% CI for the median by part/dose group using Brookmeyer and Crowley methods.

11.4.2. Pharmacokinetic/Pharmacodynamic Analyses

11.4.2.1. Pharmacokinetic Analyses

Serum concentrations for DS-8201a, total anti-HER2 antibody and MAAA-1181a will be listed, plotted, and summarized using descriptive statistics by Part (and Stage)/dose level/study day at each time point. PK parameters will be listed and summarized using descriptive statistics by Part (and Stage)/dose level. A dose selection analysis will also be conducted based on the data from Part 1, and based on comparative PK results, 2 doses will be selected for dose-finding stage of Part 1.

The population pharmacokinetic and exposure-response analysis will be conducted for all evaluable subjects in the study. An interim population PK and exposure response analysis may also be conducted based on the data from Part 1. Modeling results will be presented in separate reports.

11.4.2.2. Pharmacodynamic Analyses

Not Applicable.

11.4.2.3. Biomarker Analyses

Biomarkers will be listed and summarized using descriptive statistics.

11.4.2.4. Pharmacogenomic Analyses

Not Applicable.

11.4.3. Safety Analyses

Safety analyses in general will be descriptive and will be presented in tabular format with the appropriate summary statistics. A summary and display of TEAEs will be performed.

Terminology of the MedDRA will be used to assign system organ class (SOC) and PT classification to AEs and diseases, based on the original terms entered on the eCRF.

The incidence of TEAEs will be summarized by SOC, PT, relationship to the study treatment, and severity for each part/dose group. A by-subject listing will be provided for those subjects who experience an SAE, including death, or experience an AE associated with early withdrawal from the study or study treatment.

11.4.3.1. Adverse Event Analyses

TEAEs are AEs that occur, having been absent before the first dose of study treatment, or have worsened in severity after the initiating the study treatment. TEAEs will be coded using MedDRA and assigned grades based on version 4.03 of the National Cancer Institute's Common Terminology Criteria for Adverse Events (NCI CTCAE). The number and percentage of subjects reporting TEAEs will be tabulated by system organ class (SOC), and PT, relationship to the study treatment, and the worst CTCAE grade. Similarly, the number and percentage of subjects reporting treatment-emergent SAEs will be tabulated, as well as TEAEs leading to discontinuation of study treatments.

A by-subject AE (including treatment-emergent) data listing including but not limited to verbatim term, SOC, PT, CTCAE grade, and relationship to study treatment will be provided. Deaths, other SAEs, and other significant AEs, including those leading to discontinuation of study treatments, will be listed.

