3. STUDY DESIGN

3.1. Overall Design

3.1.1. Overview

This is Phase 2, open-label, multicenter, 2-part, study designed to investigate the anti-tumor activity as well as the safety and efficacy of DS-8201a in HER2-positive, unresectable and/or metastatic breast cancer subjects who are resistant or refractory to T-DM1.

Part 1 will enroll 120 subjects in a 2 stage design: a PK Stage and a Dose Finding Stage designed to define the RP2D that will be evaluated in Part 2.

[figure not shown]
- PK Stage: approximately 20 subjects at 7.4 mg/kg dosing, 20 subjects at 6.4 mg/kg dosing and 20 subjects at 5.4 mg/kg dosing will be randomized in a 1:1:1 ratio. Two dose levels will be selected based on the PK results.
- Dose Finding Stage: approximately 30 subjects at each dose level will be randomized in a 1:1 ratio into 1 of 2 treatment groups selected after the PK analysis. A dose selection analysis will be performed to evaluate both safety and efficacy in order to determine the optimal dose for DS-8201a.

Part 2a will continue to enroll approximately 100 subjects at the RP2D of 5.4 mg/kg (see Section 11.5) as well as the Phase 1 trial DS8201-A-J101. Part 2b will enroll an open-ended number of subjects that received T-DM1 but are not eligible for the primary analysis. This is an exploratory cohort with the objective to explore the efficacy of DS-8201a in subjects who discontinued prior T-DM1 therapy for reasons other than progression of disease. Part 2b will enroll an open-ended number of subjects. The enrollment duration of Part 2b is determined based on enrollment in Part 2a. Part 2a and Part 2b will begin enrollment simultaneously and complete enrollment when the target of approximately 100 subjects enrolled is reached for Part 2a. Approximately 10 to 15 subjects would be expected to enroll in Part 2b. The exploratory analysis for Part 2b will be performed at the same time as the primary analysis cohort including all subjects in Part 1 and Part 2a treated at the RP2D of 5.4 mg/kg.

DS-8201a will be administered [REDACTED] at a dose of 7.4 mg/kg, 6.4 mg/kg or 5.4 mg/kg every 3 weeks.

The study treatment will be continued according to the dosing criteria to derive clinical benefit in the absence of withdrawal of subject consent, PD, or unacceptable toxicity. If the study treatment is delayed more than 4 weeks from the planned date of administration, the subject will be withdrawn from the study drug (see Section 5.7.3).

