Figure 3.1: Study Design Schema of DS8201-A-U201

History of past treatment with pertuzumab will be collected for all study subjects. The study plans to enroll 100 or more subjects with history of prior pertuzumab treatment in the metastatic/advanced breast cancer setting. If after 150 subjects have been enrolled at the RP2D (20 from the PK stage, 30 from the dose finding stage and 100 from Part 2a), less than 100 such subjects have been enrolled, the study may continue to enroll subjects but only those meeting this criteria, and until at least 100 such subjects have been enrolled. This study also has a cap for subjects with moderate hepatic impairment at approximately 10 subjects (See Section 4.1, #10).

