9.3.1. Interstitial Lung Disease/Pneumonitis

9.3.1.1. Clinical Summary

As of 13 Dec 2017, 3 clinical studies have subjects dosed with DS-8201a: DS8201-A-J101, DS8201-A-U201, and DS8201-A-J202. There have been no events of ILD/pneumonitis reported in the DS8201-A-U201 and DS8201-A-J202 studies. Due to the limited number of subjects dosed and short treatment duration in these 2 studies, ILD/pneumonitis data has been summarized from the DS8201-A-J101 study.

Interstitial lung disease/pneumonitis is considered an important identified risk based on a comprehensive cumulative review of the available safety data from the DS8201-A-J101 clinical study as well as the results of potential ILD/pneumonitis cases reviewed by the independent ILD AC, available data from recent epidemiology/literature, biological plausibility, and safety information from drugs of similar class. Refer to the current IB for a summary of preliminary clinical study data.

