11.2. General Statistical Considerations

A data cut-off date for the primary analysis will be identified during Part 2.

Data in Part 1 and Part 2a will be combined by the starting dose level. Summary statistics will be presented by part/dose group. Continuous variables will be summarized by the number of observations, mean, standard deviation, median, minimum, and maximum values. Categorical variables will be summarized using frequency counts and percentages.

Assessments of change from baseline to post-treatment or the ratio of post-treatment to baseline will include only those subjects with both baseline and post-treatment measurements. The last non-missing value of a variable taken before the first dose of study treatment will be used as the baseline value, unless otherwise specified. In general, missing or dropout data will not be imputed for the purpose of data analysis, unless otherwise specified.

Analyses of ORR, DCR, and CBR will be performed on the Response Evaluable Set. The other efficacy analyses will be performed on the Full Analysis Set (FAS). Safety analyses will be performed using the Safety Analysis Set. Analysis of PK parameters will be based on the PK Analysis Set. All other exploratory analyses will be performed based on the FAS and availability of assessment.

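### Crude ILD percentages, with later-enrolled Part 2a pooled into the 5.4 mg/kg group, can understate ILD at that dose and flatter it against 6.4 and 7.4 mg/kg if the cut-off is early

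*Combined protocol and SAP*

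**What the plan says.** Section 11.4.3.1 gives the scale for treatment-emergent events: "The number and percentage of subjects reporting TEAEs will be tabulated by system organ class (SOC), and PT". Treatment-emergent SAEs and events leading to discontinuation are handled the same way. Section 11.4.3 gives the grouping: "The incidence of TEAEs will be summarized by SOC, PT, relationship to the study treatment, and severity for each part/dose group". No person-time rate, time to onset or cumulative incidence is named for any adverse event, and Section 11.4.3.7 (exploratory safety analyses) is marked not applicable.

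Section 11.2 adds: "Data in Part 1 and Part 2a will be combined by the starting dose level". On timing it says only: "A data cut-off date for the primary analysis will be identified during Part 2".

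Section 3.1.1 builds the 150 subjects at the RP2D as "20 from the PK stage, 30 from the dose finding stage and 100 from Part 2a". Section 5.1.1 gives Part 2 a single dose, 5.4 mg/kg, so every 6.4 and 7.4 mg/kg subject belongs to Part 1.

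Section 9.3.1 treats ILD as an identified risk and sends potential cases to an independent adjudication committee. Section 2.3.2 lists events of special interest as a secondary safety endpoint. Section 11.4.3 has no analysis specific to either.

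**The concern.** A crude percentage counts a subject seen for four months the same as one seen for fourteen. That does little harm when groups have similar time at risk. Here two thirds of the 5.4 mg/kg group enter last, so at an early cut-off many are still on treatment with part of their ILD risk ahead of them. The 6.4 and 7.4 mg/kg groups contain no such subjects.

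Two readings of the final table are exposed. The ILD percentage at 5.4 mg/kg can be too low as an estimate of risk over a full course. The comparison across doses can also show a gradient that comes partly or wholly from enrolment order. ILD matters most here because Section 1.3 reports two fatal cases adjudicated as drug-related. The protocol is itself cautious about early counts: Section 9.3.1.1 turns to the Phase 1 study for ILD data, giving as its reason "Due to the limited number of subjects dosed and short treatment duration in these 2 studies".

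**Working it through.** **The plan's own figures.** The protocol gives no figure for event incidence or follow-up by dose. Its only design calculation concerns response (Section 11.6: 98.2% and 91.6%). It reproduces as P(X ≥ 41) = 0.9816 and P(X ≥ 45) = 0.9159 for X binomial with n = 150 and p = 0.35, but does not bear on this point.

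**Inputs from the protocol**
- Stage sizes (Section 3.1.1): PK Stage, "approximately 20 subjects at 7.4 mg/kg dosing, 20 subjects at 6.4 mg/kg dosing and 20 subjects at 5.4 mg/kg dosing will be randomized"; Dose Finding Stage, "approximately 30 subjects at each dose level will be randomized in a 1:1 ratio"; Part 2a, about 100.
- Accrual about 12 months; at least 10 months of follow-up projected after the last subject (Section 3.1.2).
- Most subjects receive 10 to 20 cycles of 21 days (Section 3.1.3), which is 210/30.44 = 6.9 to 420/30.44 = 13.8 months.
- Events recorded to 40 (+7) days after the last dose (Section 9.1).

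**Assumptions**
- 60 + 60 + 100 = 220 subjects accrue evenly over 12 months: PK Stage months 0–3.3, Dose Finding 3.3–6.5, Part 2a 6.5–12.
- Treatment duration d is uniform on 6.9–13.8 months.
- 6.4 mg/kg is the second dose carried into Dose Finding (the protocol does not say).
- ILD risk is 10% at 12 months and **identical at every dose**: F(t) = 1 − 0.9^(t/12) for a constant hazard, or 1 − 0.9^((t/12)²) for a rising one.

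**Formulas.** For a block entering at time e, with cut-off c and window w after the last dose, the crude proportion is the mean of F(min(d + w, c − e)). Call the block values PK, DF and P2a. Then:
- 7.4 mg/kg = PK
- 6.4 mg/kg = (20·PK + 30·DF)/50
- 5.4 mg/kg = (20·PK + 30·DF + 100·P2a)/150

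Example (cut-off 6 months after last enrolment, w = 0, constant hazard): (20 × 8.67 + 30 × 8.60 + 100 × 7.03)/150 = 7.56% at 5.4 mg/kg against 8.67% at 7.4 mg/kg, ratio 0.87.

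| Cut-off after last enrolment | w | Hazard | PK % | DF % | P2a % | 5.4 mg/kg % | 5.4/6.4 | 5.4/7.4 |
|---|---|---|---|---|---|---|---|---|
| 3 months | 0 | constant | 8.62 | 7.83 | 4.88 | 5.97 | 0.733 | 0.692 |
| 3 months | 0 | rising | 7.65 | 6.20 | 2.52 | 3.94 | 0.581 | 0.515 |
| 3 months | 47 d | constant | 9.63 | 8.27 | 4.90 | 6.20 | 0.704 | 0.644 |
| 3 months | 47 d | rising | 9.44 | 6.87 | 2.54 | 4.33 | 0.548 | 0.458 |
| 6 months | 0 | constant | 8.67 | 8.60 | 7.03 | 7.56 | 0.876 | 0.872 |
| 6 months | 0 | rising | 7.76 | 7.61 | 5.05 | 5.92 | 0.772 | 0.763 |
| 6 months | 47 d | constant | 9.90 | 9.56 | 7.27 | 8.08 | 0.833 | 0.816 |
| 6 months | 47 d | rising | 10.04 | 9.30 | 5.41 | 6.80 | 0.709 | 0.678 |
| 10 months | 0 | constant | 8.67 | 8.67 | 8.48 | 8.54 | 0.985 | 0.985 |
| 10 months | 0 | rising | 7.76 | 7.76 | 7.38 | 7.51 | 0.967 | 0.967 |
| 10 months | 47 d | constant | 9.90 | 9.90 | 9.37 | 9.55 | 0.964 | 0.964 |
| 10 months | 47 d | rising | 10.04 | 10.04 | 8.93 | 9.30 | 0.926 | 0.926 |

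The ratios hardly depend on the assumed 10%. Taking 3.4% instead (the 5 of 148 ILD or pneumonitis cases in Section 1.1.1.5) changes none of them by more than about 0.01.

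**Would a patient-year rate suffice?** Dividing first events by time at risk (the mean of the integral of 1 − F up to min(d + w, c − e)) gives a 5.4/7.4 ratio of exactly 1 under the constant hazard. Under the rising hazard with the 47-day window it is 0.71, 0.83 and 0.96 at the 3, 6 and 10 month cut-offs. It reduces the bias without removing it.

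**Chance.** The exact 95% interval around an observed 10% is 1.2–31.7% at n = 20, 3.3–21.8% at n = 50 and 5.7–16.0% at n = 150.

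**The case against.** The strongest reply is that the protocol's own inputs nearly dissolve the problem. If the cut-off comes 10 months after the last subject and treatment lasts 10 to 20 cycles, the ratio is 0.93 or higher. Clinical benefit requires more than 6 months of stable disease, and response is to be reported at times up to 12 months, so a 3-month cut-off looks unlikely. This stands as a limit on size. But Section 3.1.2 describes study follow-up and does not set a condition on the primary cut-off, which Section 11.2 leaves open.

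Other replies carry partial weight:
- The part/dose group wording may let Part 1 be shown apart from Part 2a. It is ambiguous beside the pooling sentence, and a separate Part 2a percentage would still be immature.
- Exposure and treatment duration are summarized (Section 11.3), and exposure-response analyses cover safety endpoints (Section 11.4.2.1). The first is not linked to events, and the second is not specified as a time-at-risk analysis.
- Section 11.7 defers safety methods to an SAP. The text supplied contains no SAP methods, so the gap can be asserted for the protocol only.

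A reader might infer more than the documents support:
- *That ILD at 5.4 mg/kg is understated, or that any dose difference comes from follow-up alone.* There is no cut-off date, exposure by dose or ILD hazard over time in the protocol, and Section 9.3.1.1 gives no such hazard. A true dose effect may exist.
- *That the choice of dose was biased.* Section 11.5 places that analysis in the Dose Finding Stage, and 5.4 mg/kg is already fixed for Part 2.
- *That all adverse events are affected alike.* The argument applies to events whose risk continues during treatment, and it is made here for ILD.
- *That the bias stays large at 10 months.* Exponential treatment times give 5.4/7.4 ratios of 0.65 to 0.88 there. They put at most 25% of subjects between 10 and 20 cycles (with x the share still treated at 10 cycles, x − x² peaks at 0.25), which contradicts the protocol's expectation for most subjects.

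**Conclusion.** The point holds as a conditional weakness in how ILD will be presented. Crude percentages, pooling by starting dose and an open cut-off together allow the ILD figure at 5.4 mg/kg to be too low, and to look lower than at 6.4 and 7.4 mg/kg, with no difference in hazard. Under the stated assumptions the 5.4/7.4 ratio is about 0.5 to 0.7 at a 3-month cut-off, 0.7 to 0.9 at 6 months and 0.93 to 0.98 at 10 months. The direction favours 5.4 mg/kg in every case examined; the size depends mainly on the cut-off, then on whether the hazard rises.

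The absolute gaps are small beside sampling error: 1.1 points in the 6-month example, against 5 points for a single event among about 20 subjects at 7.4 mg/kg. The change is worth making because it is cheap and ILD is the main identified harm.

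**What to change.** In Section 11.4.3.1, add the following for adjudicated ILD and the other events of special interest:

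1. Cumulative incidence of the first event from first dose, by starting dose, at fixed times such as 6 and 12 months. Use the Aalen-Johansen estimator, with death and the end of the event reporting period as competing events and subjects still at risk censored at the cut-off. Give numbers at risk. State that doses are compared on this measure.
2. The same display for Part 1 alone by randomized dose. This avoids mixing in the non-randomized Part 2a and the drug-product change expected around the start of Part 2 (Section 5.2.4).
3. Exposure-adjusted rates beside the crude percentages, labelled supportive only, because they do not correct a hazard that rises with time.

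Stating a minimum follow-up for the primary cut-off in Section 11.2 would also bound the problem.

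The cost is a few extra tables and a figure from event onset and dosing dates already collected. The reported ILD figure at 5.4 mg/kg may become less favourable. At an early cut-off the 12-month estimate for that dose would rest mostly on its 50 Part 1 subjects and be less precise. No dosing or clinical rule changes.

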11.4.3.2. Clinical Laboratory Evaluation Analyses

Descriptive statistics will be provided for the central clinical laboratory results by scheduled time of evaluation, as well as for the change from baseline. In addition, the change from baseline will be summarized for the maximum and minimum post-treatment values.

Abnormal clinical laboratory results will be graded according to NCI CTCAE version 4.03, if applicable, and the grade will be presented in a by-subject data listing. A shift table, presenting the 2-way frequency tabulation for baseline and the worst post-treatment value according to the NCI CTCAE grade, will be provided for clinical laboratory tests.

All clinical laboratory test results and abnormal clinical laboratory test results deemed of clinical significance or of Grade 3 or 4 will be listed.

11.4.3.3. Vital Sign Analyses

Descriptive statistics will be provided for the vital signs measurements by scheduled time of evaluation, as well as for the change from baseline. In addition, the change from baseline will be presented for the maximum and minimum post-treatment values. All vital sign data will be also listed.

11.4.3.4. Electrocardiogram Analyses

Descriptive statistics will be provided for ECG parameters and changes from baseline by scheduled time of evaluation, including the maximum post-treatment values and the values at the EOT Visit. In addition, the number and percentage of subjects with ECG interval values meeting the criteria will be tabulated (eg, QTc \leq 450 ms, > 450 to \leq 480 ms, > 480 ms to \leq 500 ms, and > 500 ms). The QT intervals will be corrected for heart rate by **Fridericia's formula (QTcF $QT/[RR]^{1/3}$)**. ECG data will also be listed.

11.4.3.5. Physical Examination Analyses

Physical examination findings will be listed.

11.4.3.6. Concomitant Medication Analyses

Concomitant medications will be coded using the World Health Organization drug dictionary (most recent version). Number and percentage of subjects taking concomitant medications will be summarized. Concomitant medications will also be listed.

11.4.3.7. Exploratory Safety Analyses

Not applicable.

11.4.3.8. Immunogenicity (Anti-Drug Antibody, ADA) Analyses

Immunogenicity will be assessed through characterization of incidence and titer of ADA. The number and percentage of subjects will be calculated for the presence or absence of development of ADA after the start of administration, defining subjects who are negative for ADA at all-time points as negative and subjects who are positive for ADA at least one time point post drug treatment as positive. The raw values and change from baseline for ADA titers will be summarized by time point and treatment group using descriptive statistics.

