4.1. Inclusion Criteria

Subjects must satisfy all of the following criteria to be included in the study:

1. Men or women ≥ 20 years old in Japan and Korea, ≥ 18 years old in the US (for other countries, please follow the reference²)
2. Pathologically documented breast cancer that:
 - is unresectable or metastatic;
 - has confirmed HER2 positive expression (estrogen receptor/progesterone receptor positive subjects may be enrolled if they are HER2 positive) according to American Society of Clinical Oncology College of American Pathologists (ASCO-CAP) guidelines²¹ evaluated at a Central Laboratory. See Laboratory Manual for details.
3. Subjects must have an adequate tumor sample available for confirmation of HER2 status by Central Laboratory (based on most recent tumor tissue sample, see Section 6.1)
4. Subject must have breast cancer which is resistant or refractory to T-DM1 with documented clinical or radiographic progression of disease during or after treatment with T-DM1
 - For Part 2b, subjects must have discontinued treatment with T-DM1 for reasons other than resistant or refractory disease
5. Presence of at least one measurable lesion per RECIST version 1.1
6. LVEF $\geq 50\%$
7. ECOG PS 0 or 1
8. Adequate bone marrow function, defined as:

² <https://hrpo.wustl.edu/wp-content/uploads/2015/01/5-Determining-Legal-Age-to-Consent.pdf>

- Absolute neutrophil count (ANC) $\geq 1.5 \times 10^9/L$ (G-CSF administration is not allowed within 1 week prior to screening assessment)
 - Platelet count $\geq 100 \times 10^9/L$ (Platelet transfusion is not allowed within 1 week prior to screening assessment)
 - Hemoglobin level ≥ 9.0 g/dL (Red blood cell transfusion is not allowed within 1 week prior to screening assessment)
9. Adequate renal function, defined as:
- Creatinine clearance ≥ 30 mL/min, as calculated using the Cockcroft Gault equation (Section 17.1), ($\{140 - \text{age in years}\} \times \{\text{actual weight in kg}\}$) divided by ($\{72 \times \text{serum creatinine in mg/dL}\}$ multiplied by 0.85 if female)
10. Adequate hepatic function, including mild-moderate hepatic impairment defined as the following:
- Normal hepatic function to mild hepatic dysfunction: Total bilirubin $\leq 1.5 \times \text{ULN}$ or $< 3 \times \text{ULN}$ in the presence of documented Gilbert's syndrome or liver metastases at baseline and aspartate transaminase (AST)/alanine transaminase (ALT) $\leq 5 \times \text{ULN}$

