6.6. Follow-up

Forty days (+7 days) after last study drug administration or before starting new anticancer treatment, whichever comes first, the following procedures will be performed as specified in the Schedule of Events. If EOT is > 40 (+7) days after last treatment, then the EOT assessments can also function as the follow-up visit.

- Vital signs (systolic and diastolic blood pressure, pulse rate, respiratory rate, body temperature and SpO₂).
- Physical examination. Weight will be recorded.
- ECOG PS.
- Hematology, blood chemistry, and troponin assessments will be performed.
- AEs and concomitant medications will be recorded.
- For subjects with positive ADA at the follow-up visit, additional serum ADA samples must be collected every 3 months (\pm 1 month) up to 1 year from the last dose of study drug, or until the ADA becomes negative, or until the ADA titer becomes less than baseline (applicable when pre-existing ADA is observed), or until the subject starts another therapy for cancer, or withdraws consent from the study, whichever occurs first.

Subjects will also be assessed every three months (\pm 14 days), from the date of follow-up visit, for survival and subsequent anticancer therapy until death, withdrawal of consent, loss to follow-up, or study closure; whichever occurs first. This information may be collected in a visit or via phone contact, or (as necessary for survival status, in the case of withdrawal of consent or loss to follow-up) from public records as allowed by law.

Further follow-up may be required for ongoing AEs (see Section 9.1).

Table 6.1: Schedule of Events – Part 1 PK Stage

	Tissue Screen	S C R (-14 d or as not ed)	Cycle 1					Cycle 2			Cycle 3			Cycle 4 and subsequent cycles		Every 6 wks (±7 days)	EOT (a)	40-day FU (±14 days)	q3 mo FU (±14 days)					
			Day 1		Day 2	Day 4	Day 8	Day 15	Day 22 ^v	Day 1		Day 22 ^v	Day 1		Day 22 ^v									
			BI	EOI			(±1 day)	(±1 day)	(±2 days)	BI	EOI	(±2 days)	BI	EOI	(±2 days)					BI	EOI			
Informed Consent (may sign)	•	•																						
Administer DS 8201a			•						•			•			•									
Medical		•																						
Demograp		•																						
Pregnancy		•																	•					
Vital Signs		•	•	•		•	•		•	•		•	•		•			•	•					
Physical		•	•						•			•			•			•	•					
SpO2		•	•						•	(d)		•	(d)		•	(d)		•	•					
Inclusion/Exclusion		•																						
Height		•																						
Weight, ECG, BP		•	•						•			•			•			•	•					

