- n For subjects with positive ADA at F/U visit, additional serum ADA samples must be collected every 3 months (\pm 1 month) up to 1 year from the last dose of study drug, or until the ADA becomes negative, or until ADA titer becomes less than baseline (applicable when pre-existing ADA was observed), or until the subject starts another therapy for cancer, or withdraws consent from the study, whichever occurs first.
- o Within 28 days before randomization/registration.
- p Before administration at every 2 cycles from Cycle 3 (Cycle 3, 5, 7, 9, etc).
- q Echo or MUGA scan assessments (note: the same test must be used for the subject throughout the study) will be performed at Screening and every 4 cycles (\pm 7 days) (Cycle 5, 9, 13, etc)
- r ECGs will be taken in close succession, approximately 3 minutes apart, while in a supine/semi-recumbent position.
- s An MRI of the brain is mandatory for all subjects who were enrolled with baseline stable brain metastases. Subjects without brain metastases do not need additional brain scans for tumor assessment unless clinically indicated.
- t Ophthalmologic assessments to include visual acuity testing, slit lamp examination and funduscopy will be performed at Day 1 of Cycle 2 (within 3 days before administration) and every 4 cycles (\pm 7 days) thereafter (Day 1 Cycle 2, 6, 10, 14, etc).
- u Archived tissue appropriate for central laboratory HER2 testing. If archived tissue is not available, fresh biopsy is required. Up to 5 additional slides are requested for optional biomarker analysis.
- v Based on no delays and a 21-day cycle, Day 22 should be the same as Day 1 of the next cycle. In the event that there is a delay in the start of the next cycle, the goal is to still obtain the PK sample on Day 22 of the earlier cycle.
- w DS-8201a is to be administered every 3 weeks \pm 2 days unless discontinuation criteria are required.
- x For subjects who sign only the Informed Consent Form for tissue screening, report only serious adverse events (SAEs) directly related to tissue screening procedure (ie, tumor biopsy). Unless documentation of other AEs is required by local law, only SAEs directly related to tumor biopsy will be recorded during tissue screening. For suspected ILD/pneumonitis, treatment with study drug should be interrupted pending evaluation. Evaluations should include:
- High resolution CT
 - Pulmonologist consultation
 - Pulmonary function tests and pulse oximetry (SpO₂)

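### The ADA incidence rule counts any post-dose positive as development of ADA, so subjects already positive before dosing are counted as new cases

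*Combined protocol and SAP*

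**What the plan says.** Section 11.4.3.8 plans the number and percentage of subjects for "presence or absence of development of ADA after the start of administration". It fixes the two classes in one sentence. The negative class is set by the words "defining subjects who are negative for ADA at all-time points as negative". The positive class, which alone feeds the reported incidence, takes in "subjects who are positive for ADA at least one time point post drug treatment as positive". The section then adds a separate descriptive output: "The raw values and change from baseline for ADA titers will be summarized by time point and treatment group using descriptive statistics".

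Other sections bear on this rule:

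- **Baseline sample.** Table 6.1 (footnote m) and Table 6.2 (footnote l) schedule an ADA sample before the Cycle 1 Day 1 infusion, so each subject's status before treatment should be known.
- **Titers.** Section 8.3 describes a tiered assay that ends in titer determination.
- **Pre-existing ADA.** Section 6.6 lets extended ADA sampling stop, among other reasons, "until the ADA titer becomes less than baseline (applicable when pre-existing ADA is observed"). Table 6.1 footnote n and Table 6.2 footnote m repeat this condition.
- **Status of the endpoint.** Section 2.3.2 lists ADA as a safety endpoint. Section 11.2 presents summaries by part/dose group.
- **Definitions.** Section 11.7 leaves statistical definitions to a SAP that is to be finalized before database lock. No text in the supplied documents replaces the rule in Section 11.4.3.8.

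**The concern.** The stated target and the rule do not match. Development of ADA after the start of treatment is a change from the subject's own starting point. The rule looks only at whether any post-dose sample is positive, so it measures post-dose prevalence and labels it incidence.

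The follow-up rule in Section 6.6 does judge a subject with pre-existing ADA against the baseline titer. Section 11.4.3.1 applies the same logic to adverse events, which count as treatment-emergent only if they were absent before dosing or worsened afterwards. The ADA percentage is the exception.

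Pre-existing reactivity is a case to plan for. Section 4.1 (criterion 4) and Section 3.1.1 show that every subject in every part has had T-DM1, and Section 1.1.1.2 says the study antibody shares its amino acid sequence with trastuzumab. The documents do not show that this exposure produces positives in this assay, so it is a reason to define the case and no evidence of how often it occurs.

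At stake is the reading of one safety result: the reported immunogenicity of DS-8201a would mix antibodies that subjects brought into the trial with antibodies that arose on treatment.

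**Working it through.** The plan states no ADA rate, so there is no figure to reproduce. The check is to apply the rule to each possible type of subject and then size the difference.

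**1. The rule applied to each type of subject**

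| Before dosing | After dosing | Class under Section 11.4.3.8 | Developed ADA on treatment? |
|---|---|---|---|
| Negative | Always negative | Negative | No |
| Negative | At least one positive | Positive | Yes |
| Positive | Positive, titer rises | Positive | Yes (boosted) |
| Positive | Positive, titer unchanged or lower | Positive | **No** |
| Positive | Always negative | Neither class, if the pre-dose sample is one of the time points | No |

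The fourth row is the miscount. The fifth is a secondary gap that depends on whether the pre-dose sample is meant to be included in the negative definition.

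**2. Size in general form**

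Take subjects with a baseline sample and at least one post-dose sample. Let

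- b = share positive at baseline;
- s = share of baseline positives who are positive again without a titer rise;
- r = share of baseline positives with a titer rise (s + r ≤ 1);
- t = share of baseline negatives with at least one post-dose positive.

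Then:

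- rate under the rule = (1 − b)t + b(s + r)
- treatment-emergent rate = (1 − b)t + br
- overstatement = b × s, which cannot exceed b

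None of b, s, r or t is in the documents. The values below are assumptions.

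| b | Overstatement, s = 50% | Overstatement, s = 100% |
|---|---|---|
| 0% | 0 points | 0 points |
| 1% | 0.5 | 1 |
| 3% | 1.5 | 3 |
| 5% | 2.5 | 5 |
| 10% | 5 | 10 |

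As an example, take b = 5%, s = 100%, r = 0 and t = 2%. The rule gives 0.95 × 2% + 5% = 6.9%, against a treatment-emergent rate of 0.95 × 2% = 1.9%.

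**3. Effect of one such subject at the planned group sizes**

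This step needs no prevalence. Sizes come from Section 3.1.1, with Part 1 and Part 2a combined by starting dose as in Section 11.2, and assume that every planned subject has both samples.

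- RP2D: 20 + 30 + 100 = 150, so 1/150 = 0.67 points
- Other dose in the Dose Finding Stage: 20 + 30 = 50, so 1/50 = 2.0 points
- Dose not taken forward: 20, so 1/20 = 5.0 points
- Part 2b: 10 to 15 expected, so 1/15 to 1/10 = 6.7 to 10.0 points

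The groups sum to 230 to 235, which agrees with the planned total of about 230.

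**The case against.** The strongest reply is that the planned titer table already exposes the problem. If titers exist only for confirmed positives, which is the natural reading of Section 8.3 though not stated outright, then the number of baseline titers is the number of baseline positives. The change-from-baseline rows would then show how many of them were still positive at each visit and whether titers rose. Since the overstatement cannot exceed baseline prevalence, a careful reader could bound it. This stands, but the table is by time point and group. It reclassifies nobody, and the reported percentage stays as the rule makes it.

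Second, nothing in the documents shows that any subject is positive before dosing; the wording on pre-existing ADA is conditional, and the 10% ceiling used here is an assumption. That also stands. The per-subject figures show how sensitive each group is, and say nothing about how likely the case is.

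Third, the SAP may supply a better definition. It may, and nothing here says that the final analysis lacked one. But the protocol states an explicit rule, and the supplied text does not change it.

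Fourth, no data are lost, because subjects can be reclassified later from samples already taken. This is true and keeps the point modest. A definition chosen after the results are known is still weaker than one fixed before database lock.

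**Conclusion.** The concern holds. Followed exactly, the rule in Section 11.4.3.8 counts a subject with unchanged or falling pre-existing ADA as having developed ADA, which contradicts the quantity the section says it reports. The reading of the text is firm; the practical size is not documented. The overstatement is b × s: nil if no subject is positive at baseline, and at most 10 percentage points if baseline prevalence is no more than an assumed 10%.

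The consequence is limited. Safety analyses are descriptive (Section 11.4.3). The ORR analysis, the sample size and the two probability criteria for dose selection in Section 11.5 do not use ADA. Section 11.5 also refers to an overall assessment of safety data, so an indirect role for ADA in choosing the dose cannot be ruled out from the text. The point should be corrected, but it does not threaten the trial's main conclusion.

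**What to change.** In the SAP, before database lock:

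1. Report the number and percentage of subjects who are ADA-positive at baseline as a separate line.
2. Define treatment-emergent ADA as (a) negative at baseline with at least one post-dose positive, or (b) positive at baseline with a post-dose titer above baseline by a fold set in advance from the assay's performance. The documents give no fold, so the sponsor must state and justify one.
3. Class all other baseline positives, including those positive only before dosing, as not treatment-emergent, so that every subject in the denominator falls into one class.
4. Use as denominator the subjects with a baseline and at least one post-dose ADA sample, and state how many dosed subjects this leaves out.

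The existing any-post-dose-positive percentage can stay if it is labelled as post-dose prevalence. The cost is one definition and one table. The pre-dose Cycle 1 sample and the titers are already planned, so no visit, sample or assay is added.
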